## 7.2 Prior and Concomitant Medications

Concomitant medications are all medications (or treatments) other than study drugs that are taken or received by the subject at any time during the study starting at the time that the first dose of study drug was administered through the end of study treatment. Use of all concomitant medications, including any change in therapy, will be recorded, categorized and summarized by ATC Class and Preferred Term according to WHODrug Global B3 01MAR2021. Refer to [Section 8.1.1](#) for rules of imputing partial/missing concomitant medications start and stop dates.

Prior medications are medications that are taken within 28 days prior to a subject's first dose of study drug and discontinued prior to the first dose of study drug. Prior medications will be listed.

## 7.3 Efficacy Variables

The primary efficacy measure is anti-tumor response assessed by an IRF every 8 weeks in the first 12 months of study treatment and every 12 weeks thereafter until disease progression. Assessments will also be made by the Investigator. Response criteria will be based on RECIST v1.1. Baseline efficacy assessments are required to be completed within 28 days prior to Cycle 1 Day 1. Any tumor assessment completed within 42 days prior to Cycle 1 Day 1 will be considered as baseline assessment.

The following variables are defined for AIM-HN only. Efficacy variables will be reported for the High VAF subjects as well as all VAF subjects.

### 7.3.1 Objective Response Rate (ORR)

ORR is the proportion of subjects with Best Overall Response (BOR) of a confirmed CR or confirmed PR by RECIST v1.1.

BOR is the best response recorded from the first dose date of the study drug until disease progression or death or the start of new anti-cancer therapy whichever occurs first. BOR per IRF will be assigned by IRF.

The BOR by investigator assessment will be derived based on following order: Confirmed CR > Confirmed PR > SD > PD. All other cases will be categorized as NE.

#### Confirmed Complete Response (CR):

- (CR CR) within two consecutive visits (including unscheduled visits) at least 28 days apart, or
- (CR NE CR) within three consecutive visits at least 28 days apart from the third visit to the first visit

#### Confirmed Partial Response (PR):

- (PR PR) within two consecutive visits at least 28 days apart, or
- (PR NE PR) or (PR SD PR) within 3 consecutive visits at least 28 days apart from the third visit to the first visit

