#### Stable Disease (SD):

- patient without confirmed CR or confirmed PR, but with one single assessment after 35 days from Cycle 1 Day 1 as CR or PR followed by NE (e.g. CR + NE or PR + NE), or
- patient without confirmed CR or confirmed PR, but with one single assessment after 35 days from Cycle 1 Day 1 as CR or PR as the last assessment prior to the data cutoff date (e.g. CR/PR + no further evaluation), or
- patient without confirmed CR or confirmed PR but with SD after 35 days from Cycle 1 Day 1

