#### Progressive Disease (PD):

- patient without confirmed CR or confirmed PR, or SD, but with PD

**Not Evaluable (NE):** All other cases will be categorized as NE. The reason for NE may include:

- No baseline assessment
- New anti-cancer therapy started before the first post-baseline assessment
- No post-baseline assessments or all post-baseline assessments have an overall response as NE
- CR, PR, or SD too early [REDACTED]

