### 7.3.3 Duration of Response (DOR)

DOR (months) is defined as the time from the date of first response (CR or PR) to the date of progression of disease or death of any cause, whichever occurs first, in patients with a confirmed CR or PR, i.e., (date progression of disease or death – date of first CR or PR + 1)/30.4375.

The censoring rules for DOR is identical to it for PFS as specified in [Table 1](#).

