## 9.7.2 Key Secondary Endpoints and Other Secondary Endpoints for AIM-HN

DOR, PFS, and OS will be summarized using the Kaplan-Meier (KM) ([Kaplan and Meier 1958](#)) estimates in the AIM-HN mITT analysis set, which may also be summarized in the PPS. The 50% quartile (median) and 2-sided 95% confidence interval time to event endpoint will be calculated by the Brookmeyer and Crowley method ([Brookmeyer R and Crowley JJ, 1982](#)) with log-log transformation. The 6-month and 9-month progression-free survival rate, and 12-month survival rate will be estimated as well. A KM plot for each endpoint will be presented as applicable.

TTR will be summarized descriptively by summary statistics.

Response related efficacy endpoints, including TTR, by independent review facility and investigator assessment will also be summarized.

These analyses will be repeated for high VAF subjects and all VAF subjects.

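### The SAP's investigator best-response rules do not let a CR confirm an earlier PR, so some PR-then-CR subjects are lost from the supportive investigator ORR, TTR and DOR

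*SAP*

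**What the plan says.** SAP 7.3.1 has two routes to BOR. The IRF assigns its own. For the investigator, the SAP gives a derivation: "The BOR by investigator assessment will be derived based on following order: Confirmed CR > Confirmed PR > SD > PD", with everything else classed as NE. The definitions under it are explicit visit patterns.

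- **Confirmed CR:** CR-CR at consecutive visits, or CR-NE-CR, with at least 28 days between the first and last visit.
- **Confirmed PR:** "PR PR) within two consecutive visits at least 28 days apart", or "PR NE PR) or (PR SD PR) within 3 consecutive visits", again with at least 28 days from first to last.
- **SD** (no confirmed response): a response "with one single assessment after 35 days from Cycle 1 Day 1 as CR or PR followed by NE"; a response that is the last assessment before the cutoff; or an SD reading after day 35.
- **PD:** "patient without confirmed CR or confirmed PR, or SD, but with PD".

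SAP 7.3.2 and 7.3.3 limit TTR and DOR to confirmed responders (for DOR: "whichever occurs first, in patients with a confirmed CR or PR"). SAP 9.7.1 summarises the investigator ORR, and SAP 9.7.2 says that the response-related endpoints "by independent review facility and investigator assessment will also be summarized". Protocol 6.2.1 and SAP 5.1 call the investigator assessment supportive.

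**The concern.** Every confirmed-PR pattern ends in PR. A subject whose PR deepens to CR at the next scan, and whose CR is not itself confirmed, satisfies neither response definition. The rules accept an intervening worse reading (PR-SD-PR) but not a better second reading (PR-CR). Three investigator summaries are affected at once, and for ORR the error can go only one way, because it can only remove responders. In an open-label single-arm trial the investigator ORR is read against the IRF ORR, so this derivation could produce a disagreement between the two that is purely a coding artefact.

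There are two lesser points in the same rules. An unconfirmed response after day 35 that goes straight to PD, with no SD reading and no NE after the response, is labelled PD, although SD-PD and PR-NE-PD are both SD. And the words *one single assessment* in the SD definition can mean exactly one or at least one, so some sequences have two possible classifications.

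**Working it through.** The documents give no figure on this point, so there is none to reproduce. The check applies the written rules to sequences of scan results.

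**Inputs**

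- The rules of SAP 7.3.1 as set out above.
- Scans every 8 weeks in the first 12 months (SAP 5.1), that is days 56, 112, 168 and 224. The first scan is past day 35 and consecutive scans are 56 days apart, so the 35-day and 28-day conditions are always met.
- For scale only: 80 subjects, the planned per-protocol minimum, and the hypothesised ORR of 30% (both in the Protocol synopsis).

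**Step 1: named sequences.** The two middle columns are the two readings of *one single assessment*.

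| Sequence | SAP, exactly one | SAP, at least one | With the fix |
|---|---|---|---|
| PR-PR-PD | confirmed PR | confirmed PR | confirmed PR |
| PR-SD-PR-PD | confirmed PR | confirmed PR | confirmed PR |
| PR-PR-CR | confirmed PR | confirmed PR | confirmed PR |
| PR-CR-CR | confirmed CR | confirmed CR | confirmed CR |
| PR-CR | NE | SD | confirmed PR |
| PR-CR-PD | PD | PD | confirmed PR |
| PR-NE-CR-PD | PD | SD | confirmed PR |
| PR-SD-CR-PD | SD | SD | confirmed PR |
| PR-PD | PD | PD | SD |
| PR-NE-PD | SD | SD | SD |
| SD-PD | SD | SD | SD |

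**Step 2: all short sequences.** There are 425 sequences of one to four assessments drawn from CR, PR, SD and NE, with PD allowed only as the last. Leaving out those that step back from CR to PR or SD, which is a choice, 275 remain.

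- 45 contain PR-CR, PR-NE-CR or PR-SD-CR.
- 20 of these are responders anyway, because they also contain a confirming pair. The other 45 − 20 = 25 are non-responders on both readings.
- Classes of the 25: 12 SD, 9 NE and 4 PD if the phrase means exactly one; 23 SD and 2 PD if it means at least one.
- 14 of the 275 change class with the reading of the phrase.
- With the fix, all 25 become confirmed PR, 6 response-then-PD sequences move from PD to SD, and no sequence depends on the reading.

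These are counts of possible patterns, not of patients.

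**Step 3: scale per subject.** One subject in 80 is 100/80 = 1.25 percentage points. Exact (Clopper-Pearson) 95% intervals, the method of SAP 9.7.1:

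- 24/80 = 30.0% (20.3 to 41.3)
- one lost: 23/80 = 28.75% (19.2 to 40.0)
- two lost: 22/80 = 27.5% (18.1 to 38.6)
- three lost: 21/80 = 26.25% (17.0 to 37.3)

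**The case against.** The strongest reply accepts the literal reading and disputes its weight.

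- *RECIST v1.1 governs.* SAP 7.3 and 7.3.1 cite RECIST v1.1, and the Protocol's RECIST appendix is not in the text available here. A programmer might treat the listed patterns as minimum examples. This does not stand: the SAP gives a closed list with a catch-all, and a general citation does not override it. Code that follows the SAP exactly loses these subjects.
- *The category order is not contradicted.* The order ranks final BOR categories; it does not say that a CR reading at one visit counts as a PR reading. That is fair. The finding rests on the pattern list and on its asymmetry with PR-SD-PR, not on the order.
- *Most of the 25 would be rescued.* Of the 25, 13 end in CR with no further scan and 5 end in CR-NE. One more CR scan would make all 18 a confirmed CR. Only 7 are beyond rescue that way: six end in PD and one is PR-CR-NE-NE. The Protocol continues imaging until progression and provides for scans to confirm response. This stands: the realistic loss is mainly a first PR, then a CR, then PD at the next scan or no further evaluable scan.
- *The enumeration is selective.* It is. Over all 425 sequences, 38 rather than 14 depend on the reading, and 10 (exactly one) or 8 (at least one) rather than 6 move from PD to SD. The counts show that the gap exists, not how often it occurs.
- *The 80 is hypothetical.* It is. SAP section 3 refers to early closure of the study and gives no achieved denominator.
- *The response-then-PD label affects no endpoint.* Correct; it is a matter of consistent BOR tabulation.

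**Conclusion.** The concern holds, as a minor one. As written, the rules misclassify a subject with a PR followed by an unconfirmed CR, and no other confirming pair, as a non-responder, and remove that subject from the investigator ORR, TTR and DOR. The response-then-PD rule and the ambiguous phrase affect BOR labels only. Neither the primary analysis nor any key secondary IRF analysis is touched.

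The size in this trial cannot be derived from the documents. It is the number of such subjects, probably few, divided by the actual denominator. The 1.25 points per subject assumes 80 subjects, and the starting rate of 30% is the design hypothesis. The conclusion rests on the SAP's own wording, with assessments spaced so that the 28-day and 35-day conditions are met.

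**What to change.** Make three edits to SAP 7.3.1:

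1. Add to confirmed PR: PR-CR at two consecutive visits at least 28 days apart, and PR-NE-CR or PR-SD-CR over three consecutive visits with at least 28 days from the first to the third.
2. Add to SD: an unconfirmed CR or PR after 35 days from Cycle 1 Day 1 that is followed by PD.
3. In the SD definition, replace *one single assessment* with *at least one assessment*.

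The cost is a few lines of SAP text and the matching programming of investigator BOR; no new data are needed. SAP section 2 has the final version approved before database lock, so the edits belong there. After that they would have to be reported as a deviation in the CSR.

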#### Stable Disease (SD):

- patient without confirmed CR or confirmed PR, but with one single assessment after 35 days from Cycle 1 Day 1 as CR or PR followed by NE (e.g. CR + NE or PR + NE), or
- patient without confirmed CR or confirmed PR, but with one single assessment after 35 days from Cycle 1 Day 1 as CR or PR as the last assessment prior to the data cutoff date (e.g. CR/PR + no further evaluation), or
- patient without confirmed CR or confirmed PR but with SD after 35 days from Cycle 1 Day 1

#### Progressive Disease (PD):

- patient without confirmed CR or confirmed PR, or SD, but with PD

**Not Evaluable (NE):** All other cases will be categorized as NE. The reason for NE may include:

- No baseline assessment
- New anti-cancer therapy started before the first post-baseline assessment
- No post-baseline assessments or all post-baseline assessments have an overall response as NE
- CR, PR, or SD too early [REDACTED]

### 7.3.2 Time to Response (TTR)

TTR (months) is defined as the time from the date of the first dose of study treatment to the date of the first response (CR or PR), whichever occurs first, in patients with a confirmed CR or PR, i.e., (date of assessment of first CR or PR – first dose date + 1)/30.4375.

### 7.3.3 Duration of Response (DOR)

DOR (months) is defined as the time from the date of first response (CR or PR) to the date of progression of disease or death of any cause, whichever occurs first, in patients with a confirmed CR or PR, i.e., (date progression of disease or death – date of first CR or PR + 1)/30.4375.

The censoring rules for DOR is identical to it for PFS as specified in [Table 1](#).

### 7.3.4 Progression-free Survival (PFS)

PFS (months) is defined as the time from the first dose of the study drug to the first documented disease progression (PD) or death, whichever comes first. If a patient has not progressed or dies at the time of interim or final analysis (up to the date of data cutoff), PFS will be censored on the date of the last tumor assessment (up to the data cutoff). The censoring rules and censoring hierarchy for PFS is specified in [Table 1](#).

The PFS time will always be derived based on the tumor scan dates, not the assessment dates or visit dates.

**Table 1 PFS Censoring Rules**

Hierarchy Censoring	Situation	Date of Event or Censor	Event / Censor
1	No baseline radiological tumor assessment (confirmed measurable disease per RECIST v1.1) available	Treatment start date	Censor
5	No post baseline tumor assessment available and no death reported within 2 scan intervals following treatment start date	Treatment start date	Censor
	No post baseline tumor assessment available but death reported within 2 scan intervals following treatment start date	Date of death	Event
6	No tumor progression and no death reported within 2 scan intervals following last adequate tumor assessment	Date of last adequate assessment	Censor
	No tumor progression but death reported within 2 scan intervals following last adequate tumor assessment	Date of death	Event
	Tumor progression documented within 2 scan intervals following previous adequate tumor assessment	Date of progression	Event
3	Tumor progression documented after 2 scan intervals following previous adequate tumor assessment	Date of previous adequate assessment	Censor
2	New anticancer treatment started and no tumor progression	Date of previous adequate assessment prior to new therapy	Censor
4	No tumor progression and patient lost to follow-up or withdrawal of consent	Date of last adequate assessment	Censor

Notes: Adequate tumor assessment refers to a baseline assessment or a post-baseline assessment with an overall response of CR, PR, SD, non-CR/non-PD, or PD.

If target, non-target, and new lesion assessments have different dates within a visit, then the earliest of those dates will be considered as the date of the tumor assessment if the assessment for that visit is PD; otherwise, the latest date will be used.

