### The 2 scan intervals are defined as below:

The 2 scan interval from following treatment start date is 119 days (= 16 weeks + 7 days)

If the previous adequate tumor scan (prior to PD) was prior to 365 days, the 2 scan interval is defined as 126 days (= 16 weeks + 14 days)

If the previous adequate tumor scan (prior to PD) was on or after 365 days but prior to 469 days (= 68 weeks - 7 days), the 2 scan interval is 154 days (= 20 weeks + 14 days)

If the previous tumor scan (prior to PD) was after 469 days, the 2 scan interval is 182 days (= 24 weeks + 14 days)

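### Row 1 of the PFS censoring table can remove scanned, treated subjects from PFS, overlaps unranked event rows, and can give a negative duration when reused for DOR

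*SAP*

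**What the plan says.** SAP Section 7.3.4 defines PFS as "time from the first dose of the study drug to the first documented disease progression (PD) or death, whichever comes first". The same paragraph adds: "The censoring rules and censoring hierarchy for PFS is specified in" Table 1. The row ranked 1 in that table covers subjects with no baseline "radiological tumor assessment (confirmed measurable disease per RECIST v1.1) available". Its outcome is censoring on the treatment start date. It has no companion row for a subject who later dies or progresses, and it does not say whether local radiology or the IRF does the confirming.

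Other text bears on that row:

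- The note under Table 1 reads: "Adequate tumor assessment refers to a baseline assessment or a post-baseline assessment with an overall response of CR, PR, SD, non-CR/non-PD, or PD". Any baseline assessment qualifies, with no measurability condition.
- Three rows of Table 1 are events, and none carries a hierarchy number. One covers a subject with no post-baseline "tumor assessment available but death reported within 2 scan intervals following treatment start date", counted as an event on the date of death. The interval from treatment start is set at 119 days.
- SAP Section 9.1.1 puts every treated AIM-HN subject in the mITT set, and Section 6 specifies PFS by IRF in that set. The per-protocol set (Section 9.1.2) additionally requires measurable disease confirmed by the IRF. Entry needs only local confirmation (protocol Section 7.1.1, criterion 5).
- SAP Section 7.3.3 applies the PFS censoring rules unchanged to DOR.
- Protocol Section 12.2.1 excludes subjects without IRF-confirmed measurable disease from the mITT efficacy set, although the synopsis describes the mITT set without that exclusion. The PFS and DOR definitions in protocol Section 12.1.1 contain no measurability condition.

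**The concern.** The parenthesis widens row 1 from subjects who were never scanned to subjects who were scanned but lack confirmed measurable disease. The SAP expects such subjects to exist: an IRF filter on the per-protocol set has a purpose only if some treated subjects fail it. If row 1 governs, their observed progressions and deaths drop out of an analysis whose stated population includes them, so a per-protocol criterion enters the mITT analysis through a censoring rule.

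Three further problems follow. The note accepts non-CR/non-PD, the response category for disease followed without target lesions, while row 1 would remove the subjects who need that category. The table does not say what happens when row 1 and an event row both fit, so two programmers could produce different PFS data. And DOR, a key secondary endpoint, inherits a censor date that precedes the response.

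**Working it through.** **The SAP's own figures.** The scan intervals reproduce: 16×7+7 = 119 days, 16×7+14 = 126, 20×7+14 = 154, 24×7+14 = 182, and 68×7−7 = 469. The documents state no event count or power for PFS.

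**One subject, two rows.** Take a subject with a baseline scan, no IRF-confirmed measurable disease, no post-baseline scan, and death on day 60, counting first dose as day 1. Use the SAP's convention of (end − start + 1)/30.4375 months.

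- Row 1: 1/30.4375 = 0.03 months, censored.
- Death row (60 < 119 days): 60/30.4375 = 1.97 months, event.

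Both rows fit and no rank separates them.

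**DOR.** Take a subject followed on non-target disease only, with a confirmed CR first seen on day 57. Row 1 places the censor date at day 1, so DOR = (1 − 57 + 1)/30.4375 = −55/30.4375 = −1.8 months, which is impossible.

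**Effect on the PFS estimate.** A subject censored on day 1 leaves the risk set before the later event times, which amounts to exclusion. If a share f is affected, the change in the 6-month rate is approximately

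f × (S_rest − S_affected).

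The documents give neither f nor the medians, so both are assumed here. With exponential PFS, S(6) = 0.5^(6/median): 35.4% for a median of 4 months and 12.5% for 2 months.

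- Equal prognosis (both 4 months): f × 0 = 0 points.
- Affected subjects worse (2 against 4 months): 0.05 × 22.9 = 1.1 points and 0.10 × 22.9 = 2.3 points overstated. The rate with events counted is 0.95×35.4 + 0.05×12.5 = 34.2%, or 0.90×35.4 + 0.10×12.5 = 33.1%, against 35.4% under row 1.
- Affected subjects better (medians swapped, 4 against 2 months): the sign reverses, giving 1.1 to 2.3 points understated.

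A Kaplan-Meier simulation agrees. It used 80 subjects, exponential PFS, a 24-month cut-off and 4,000 runs per scenario, with a median of 4 months in the unaffected subjects. The 80 is only a convenient size: the protocol's 80 counts subjects who qualify for the per-protocol set.

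| Affected | Their median (months) | 6-month PFS, row 1 | 6-month PFS, events counted | Median PFS (months), row 1 / events counted |
|---|---|---|---|---|
| 4 (5%) | 4 | 35.3% | 35.2% | 4.00 / 3.95 |
| 8 (10%) | 4 | 35.5% | 35.4% | 4.02 / 3.97 |
| 4 (5%) | 2 | 35.4% | 34.3% | 4.02 / 3.82 |
| 8 (10%) | 2 | 35.4% | 33.1% | 4.03 / 3.70 |
| 12 (15%) | 2 | 35.4% | 31.9% | 4.02 / 3.56 |

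For scale, the binomial standard error at 35.4% with 80 subjects is √(0.354×0.646/80) = 5.3 points, a 95% half-width of about 10.5 points.

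**The case against.** The best defence is that the parenthesis refers to the local confirmation required at entry. Row 1 does not name the IRF, whereas the per-protocol definition does when it means the IRF. Read that way, every eligible subject passes, and row 1 catches only subjects with a missing baseline or an eligibility violation. This reading is possible. The IRF reading is the more natural one because the PFS estimand is by IRF, but the row does not settle it.

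A reader might infer that row 1 contradicts the PFS definition. The documents do not support that: the definition hands censoring to Table 1, and other rows also depart from its bare wording, such as those for late progression and for new anticancer therapy. A reader might also infer that row 1 certainly overrides any later progression or death. That is the likely reading, but the hierarchy ranks only censor rows. Likewise, the conflict with the note is by implication, since row 1 does not use the term the note defines.

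Protocol Section 12.2.1 would exclude these subjects anyway, so row 1 comes close to what that section intended. That explains the rule without reconciling it with the SAP's own mITT set and estimand. Some items of SAP Section 3 are redacted, so the mITT change may be declared there. Such a declaration would not resolve the overlap inside Table 1 or the negative DOR.

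The consequences are limited. PFS is an other secondary endpoint summarised descriptively, and the DOR failure needs a rare type of responder.

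**Conclusion.** The point holds as an inconsistency and a gap in specification. As written, row 1 can discard observed progressions and deaths from mITT PFS, can fit the same subject as an event row with a different result, and can give a negative DOR. It is a minor point.

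Its size rests on assumptions, because the documents give neither the number of affected subjects nor their prognosis. At 5-10% affected, the 6-month rate changes by about 0 points under equal prognosis, is overstated by about 1-2 points if their median is 2 against 4 months, and is understated if they do better. These shifts are small beside sampling error. A reader might infer that row 1 makes PFS look better than it is; the documents give no basis for a direction. Primary ORR does not use Table 1, and OS still counts every death.

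**What to change.** Before database lock:

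1. Limit row 1 to subjects with no baseline tumour assessment at all and no death within 2 scan intervals (119 days) of treatment start. Count a death in that window as an event on its date.
2. Drop the measurability parenthesis. Subjects with a baseline scan but only non-measurable disease then follow the other rows, through non-target or new-lesion progression and death.
3. Rank the event rows against the censor rows, so that each subject has one outcome.
4. For DOR, allow no censor date before the date of first response.
5. Reconcile the protocol and SAP mITT definitions on subjects without IRF-confirmed measurable disease.

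The table changes cost one rewritten row, a ranking and a programming condition; item 5 is a wording change. The estimated PFS may shift slightly in either direction.
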